 - Must not have clinically symptomatic malignant bowel obstruction.
- **Cutaneous squamous cell carcinoma**
 - None
- **Small bowel adenocarcinoma**
 - Must not have clinically symptomatic malignant small bowel obstruction.

General Exclusion Criteria:

1. Presence of Brain metastases (unless they have been adequately treated with radiotherapy or surgery and stable for at least 30 days prior to enrollment provided patient is neurologically asymptomatic and without corticosteroid treatment for at least 7 days prior to enrollment).
2. Uncontrolled intercurrent illness including, but not limited to diabetes, hypertension, severe infection, severe malnutrition, unstable angina, Class II-IV New York Heart Association (NYHA) congestive heart failure (see Section 18.1), ventricular arrhythmias, active ischemic heart disease, or myocardial infarction within 6 months prior to enrollment.
3. History of or evidence of retinal pathology on ophthalmologic examination that is considered a risk factor for neurosensory retinal detachment, central serous chorioretinopathy, retinal vein occlusion (RVO), or neovascular macular degeneration.
4. Patients will be excluded from study participation if they currently are known to have any of the following risk factors for RVO:
 - a. Glaucoma with intraocular pressure \geq 21 mmHg
 - b. Grade \geq 2 serum cholesterol
 - c. Grade \geq 2 hypertriglyceridemia
 - d. Grade \geq 2 or symptomatic hyperglycemia (fasting)
 - e. Grade \geq 2 uncontrolled hypertension (patients with a history of hypertension controlled with anti-hypertensive medication to Grade \leq 1 are eligible)
5. Active malignancy (other than CRC) or a history of prior malignancy within the past 3 years. Adequately treated basal cell or squamous cell skin cancer, in situ cervical cancer, ductal carcinoma in situ, other low grade lesions such as incidental appendix carcinoid or any other cancer from which the patient has been disease and treatment free for two years are allowed. Prostate cancer patients on active surveillance are eligible.
6. Pregnant or nursing patients due to risk of fetal or nursing infant harm. Women/men of reproductive potential who do not agree to use an effective contraceptive method while on study and for at least 6 months after study treatment.
7. Exclusion criteria related to study medication (any cancer immunotherapy including CD137 agonists, anti-PD-1, anti-PD-L1, or anti-CTLA4 or any MEK or ERK inhibitor).

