2.9 DISEASE SPECIFIC RATIONALE

2.9.1 Appendiceal Adenocarcinoma

Appendiceal tumors are rare with an age-adjusted incidence of 0.12 cases per 1,000,000 per year. (**McCusker et al., 2002**) Metastatic appendiceal adenocarcinomas are tumors characterized by a relatively indolent natural clinical course if low-grade and very aggressive biology if high grade. (**Asare et al., 2016; Carr et al., 2016**) Even though cytoreductive surgery (CRS) with intraoperative hyperthermic intraperitoneal chemotherapy (HIPEC) is the standard therapy and results in prolonged survival in low-grade tumors, high tumor burden and medical comorbidities can exclude patients from curative intent surgery. (**Smeenk et al., 2007**) In high-grade tumors, chemotherapy is the only effective option but has limited benefit and chemotherapy in low-grade cases has shown no or little clinical benefit. (**Asare et al., 2016**) There exists an unmet need for active targeted agents in this setting. Emerging data has shown a higher frequency of KRAS mutations in low-grade appendiceal neoplasms (70%-80%) compared to high-grade tumors. (**Alakus et al., 2014; Raghav et al., 2013**) Pre-clinical data has shown that MAPK signaling pathway is upregulated in these tumors and MAPK inhibition (RDEA119) resulted in inhibition of mucinous tumor growth and prolongation of survival in xenograft models. (**Dilly et al., 2015**) In clinical setting, Selumetinib, another MAPK inhibitor, has shown promising activity in recurrent ovarian/peritoneal low-grade serous carcinoma, a tumor type which shares many features (peritoneal carcinomatosis, indolent biology, chemo-resistance, KRAS mutations etc.) with low-grade appendiceal adenocarcinomas. (**Farley et al., 2013**) Cobimetinib (Cobi) is an orally active, highly selective MEK1/2 (MAPK) inhibitor that has shown anti-tumor activity in RAS mutant xenografts. (**Garnock-Jones, 2015**) Appendiceal adenocarcinomas share many commonalities with metastatic colorectal cancer (mCRC) and is often treated as such. COTEZO is being actively investigated in a randomized phase III study in mCRC. Based on this preliminary information, we propose a proof-of-principle to explore activity of COTEZO in appendiceal adenocarcinomas.

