2.9.3 Small Bowel Adenocarcinomas

Small bowel adenocarcinomas (SBAs) are rare tumors and include one-third of all small bowel cancers, with an estimated 3,250 new cases diagnosed in the USA in 2013. Age-adjusted incidence rates of SBAs is highest among black (14.1 per 1,000,000) followed by white individuals (7.7 per 1,000,000). **(Raghav and Overman, 2013)** Owing to their rarity, anatomical proximity and some similarities to the large bowel, SBAs have frequently been grouped and treated as mCRC. **(Raghav and Overman, 2013)** Mutations in KRAS (codon 12 and 13) have been observed in 40–60% of all sporadic SBAs and this rate is comparable to that seen for CRC. Based on frequent KRAS mutations that occur in small bowel cancers, the RAS/RAF/MAPK pathway seems to have a role in small bowel carcinogenesis. Systemic chemotherapy has been regarded as the mainstay of treatment for patients with metastatic SBAs but to date no randomized trials have been done. Although, multiple agents have demonstrated activity in patients with metastatic SBAs, including 5-fluorouracil, capecitabine, oxaliplatin, cisplatin, gemcitabine and irinotecan with varying response rates, the overall survival remains poor. **(Raghav and Overman, 2013)** Exploring activity of immunotherapy, specifically in combination with immunomodulators is an area of great unmet need for this rare tumor. Initial success of COTEZO in refractory mCRC is encouraging and argues for exploring the combination in SBAs.

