5. MATERIALS AND METHODS

5.1 PATIENT SELECTION

5.1.1 Inclusion Criteria

Patients will be included in the study based on the following criteria:

- Patients must be informed of the investigational nature of this study and must be willing to give written informed consent in accordance with institutional and federal guidelines. Patients must be able to comply with the requirements and assessments of the study protocol.
- Must have histologically or cytologically documented rare tumor as defined per protocol that is metastatic or locally advanced and unresectable. Patients with locally advanced cutaneous squamous cell carcinoma that are technically resectable but in whom surgery is expected to lead to substantial function impairment or disfigurement are eligible.
- Must be refractory or intolerant to standard lines of therapy.
- Must have completed prior chemotherapy, immunotherapy, or radiation therapy at least 14 days prior to start of treatment and all toxicity must be resolved to CTCAE v4.0 Grade 1 (with the exception of CTCAE v4.0 Grade 2 neuropathy) prior to start of treatment.
- Presence of radiographically evaluable disease.
- Age \geq 18 years

- ECOG performance status ≤ 2
- Tissue Parameters:
 - a. Representative formalin-fixed paraffin-embedded (FFPE) tumor specimens in paraffin blocks (blocks are preferred) or at least 4 unstained slides, with an associated pathology report, for testing of tumor PD-L1 expression (Tumor tissue from bone metastases is not evaluable for PD-L1 expression and is therefore not acceptable).
 - b. Tumor tissue should be of good quality based on total and viable tumor content. Fine-needle aspiration, brushing, cell pellet from pleural effusion, bone metastases, and lavage samples are not acceptable. For core-needle biopsy specimens, at least three cores should be submitted for evaluation.
 - c. Patients who do not have tissue specimens meeting eligibility requirements must be willing to undergo a biopsy during the screening period.
- Adequate bone marrow function as indicated by the following as evidenced by all of the following within 14 days:
 - ANC $> 1000/\mu\text{L}$
 - Platelets $\geq 75,000/\mu\text{L}$
 - Hemoglobin $> 9 \text{ g/dL}$
- Adequate renal function, as evidenced by calculated creatinine clearance $> 30 \text{ ml/min}$ within 14 days prior to enrollment.

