5.1.2 Exclusion Criteria

- Presence of Brain metastases (unless they have been adequately treated with radiotherapy or surgery and stable for at least 30 days prior to enrollment provided patient is neurologically asymptomatic and without corticosteroid treatment for at least 7 days prior to enrollment).
- Uncontrolled intercurrent illness including, but not limited to diabetes, hypertension, severe infection, severe malnutrition, unstable angina, Class II-IV New York Heart Association (NYHA) congestive heart failure (see Section 18.1), ventricular arrhythmias, active ischemic heart disease, or myocardial infarction within 6 months prior to enrollment.
- History of or evidence of retinal pathology on ophthalmologic examination that is considered a risk factor for neurosensory retinal detachment, central serous chorioretinopathy, retinal vein occlusion (RVO), or neovascular macular degeneration.
- Patients will be excluded from study participation if they currently are known to have any of the following risk factors for RVO:
 - a. Glaucoma with intraocular pressure ≥ 21 mmHg
 - b. Grade ≥ 2 serum cholesterol
 - c. Grade ≥ 2 hypertriglyceridemia
 - d. Grade ≥ 2 or symptomatic hyperglycemia (fasting)
 - e. Grade ≥ 2 uncontrolled hypertension (patients with a history of hypertension controlled with anti-hypertensive medication to Grade ≤ 1 are eligible)
- Active malignancy (other than CRC) or a history of prior malignancy within last 3 years. Adequately treated basal cell or squamous cell skin cancer, in situ cervical cancer, ductal carcinoma in situ, other low grade lesions such as incidental appendix carcinoid, or any other cancer from which the patient has been disease and treatment free for two years are allowed. Prostate cancer patients on active surveillance are eligible.
- Pregnant or nursing patients due to risk of fetal or nursing infant harm. Women/men of reproductive potential who do not agree to use an effective contraceptive method while on study and for at least 6 months after study treatment.
- Exclusion criteria related to study medication (any cancer immunotherapy including CD137 agonists, anti-PD-1, anti-PD-L1, or anti-CTLA4 or any MEK or ERK inhibitor).
- Left ventricular ejection fraction (LVEF) $<$ institutional lower limit of normal or $< 50\%$.

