5.10.3 Determination of Sample Size

The primary endpoint is best ORR (PR or CR), measured as per RECIST 1.1. Three parallel single-stage phase II trials will be conducted. A total of 60 patients will be enrolled, i.e., 20 patients in each tumor group. Considering the rareness of the disease, the patient accrual rate is approximately 1 to 2 patients per month per tumor group.

Sample size calculation

For each tumor group, we will estimate the best ORR and its exact confidence interval (CI). When the sample size is 20, and the response rate is 0.3, the two-sided 95% exact CI using the Clopper and Pearson method will be (0.119, 0.543).

For each tumor group, we will also compare its overall best response rate to the historical control based on the current literature. Let p represent the overall best response rate, we will perform independent Binomial test against $H_0: p=0.1$ for each group, with a 1-sided type I error rate of 0.05. The sample size of 20 will provide 76% power to detect an improved best ORR being 30% compared to 10%.

Analysis Plan

The primary outcome is the best ORR since the start of treatment. For each tumor group, we will estimate the best response rate and its 95% exact confidence interval using the Clopper and Pearson method. And we will assess the efficacy of the combination treatment by performing the independent binomial test comparing the best response rate versus the historical control for each tumor group. The primary efficacy analyses will include all treated patients who have received at least one dose of study treatment and have baseline tumor assessment. Patients who do not receive at least 1 dose of therapy will be replaced.

For each tumor group, median DOR and corresponding 2-sided 95% CI will be reported. The association between the best ORR and other variables will be assessed using the Fisher's exact test. Time-to-event outcomes, including progression free survival (PFS) and overall survival (OS), will be estimated using Kaplan-Meier method. The log-rank test will be performed to test the difference in time-to-event distributions between patient groups. Cox proportional hazards model may be utilized to include multiple covariates in the time-to-event analysis.

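### The malignancy exclusion exempts colorectal cancer, which is not a study tumor, and does not exempt the three tumors under study

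*Combined protocol and SAP*

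**What the plan says.** Section 5.1.2 excludes patients with "Active malignancy (other than CRC) or a history of prior malignancy within last 3 years". General exclusion 5 of the synopsis has the same rule: "Active malignancy (other than CRC) or a history of prior malignancy within the past 3 years".

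The item then lists what is allowed:
- "Adequately treated basal cell or squamous cell skin cancer, in situ cervical cancer, ductal carcinoma in situ";
- low-grade lesions, with incidental appendix carcinoid as the example;
- "any other cancer from which the patient has been disease and treatment free for two years are allowed";
- prostate cancer under active surveillance.

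The required disease is set in Section 5.1.1: "Must have histologically or cytologically documented rare tumor as defined per protocol that is metastatic or locally advanced and unresectable". The same criterion also admits locally advanced cutaneous squamous cell carcinoma that could be resected only with serious functional or cosmetic harm. The cohorts are listed in the synopsis and in the basket-specific criteria of Sections 5.1.1 and 5.1.2. There is no CRC cohort.

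On efficacy, Section 5.10.3 states: "The primary endpoint is best ORR (PR or CR), measured as per RECIST 1.1". Each tumor group is analyzed separately with 20 patients.

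**The concern.** The parenthesis in this kind of criterion normally removes the disease under study, so that the rule bears only on second cancers. Here it removes a disease that the trial does not study and leaves the three studied diseases inside the exclusion.

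Two things are at stake. First, Section 5.6.1 requires confirmation before enrollment that every eligibility criterion is met. Staff can confirm this one only by assuming an exemption that is not written, and each enrollment is then open to question at audit. Second, once that exemption is assumed, the written rule names active CRC as a tolerated second cancer. The primary endpoint is a count of responders among 20 patients, so it matters whose lesions are being measured.

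**Working it through.** **Step 1: does anything in the item exempt the study tumor?** Each exception is set against a patient who meets the inclusion criterion.

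| Exception | Covers an active, advanced study tumor? |
|---|---|
| CRC | No; not a cohort |
| Treated basal or squamous cell skin cancer | No; requires adequate treatment |
| In situ cervical cancer, ductal carcinoma in situ | No |
| Low-grade lesions | No; the example is an incidental finding |
| Any other cancer, two years free of disease and treatment | No; the study tumor is present |
| Prostate cancer under surveillance | No |

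The basket-specific criteria add rules on surgery, prior fluorouracil-based therapy and bowel obstruction. None alters the malignancy item.

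**Step 2: can CRC be read as shorthand for the study tumors?** Section 2.9.1 says: "Appendiceal adenocarcinomas share many commonalities with metastatic colorectal cancer (mCRC) and is often treated as such". Section 2.9.3 says: "SBAs have frequently been grouped and treated as mCRC". Both describe resemblance and shared treatment between separate diseases. Cutaneous squamous cell carcinoma cannot be read as CRC at all.

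**Step 3: what follows under each reading?**
- *Literal.* Section 5.1.1 requires an active advanced study tumor and Section 5.1.2 excludes it. A patient who also has CRC is excluded too, because the study tumor is an active malignancy other than CRC.
- *Practical (study tumor implicitly exempt).* The contradiction goes away. A concurrent active CRC then passes the active-malignancy limb, and no other criterion expressly excludes it. The three-year history limb carries no CRC exemption, so a site could still use it to refuse the patient.

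**Step 4: could CRC lesions reach the endpoint?** Section 5.6.5 has all measurable and evaluable lesions assessed. Appendix 2 chooses target lesions to represent all involved organs. Neither has a step that assigns a lesion to a primary. A shrinking CRC lesion could help produce a recorded response. A stable or growing one could hide a response or trigger progression.

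**Step 5: the plan's own figure.** Inputs from Section 5.10.3: n = 20, null rate 0.10, alternative 0.30, one-sided 0.05. With X binomial, P(X ≥ 4 | 0.10) = 0.133, which is too large, and P(X ≥ 5 | 0.10) = 0.0432. The cut-off is therefore 5 responders, and power is P(X ≥ 5 | 0.30) = 0.7625. This matches the stated 76%. The eligibility wording does not enter the calculation.

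**Step 6: illustration of size.** Assumption: m of 20 patients have a recorded response that is wholly that of a CRC, with response rate q, and patients are independent. The quantity is P(A + B ≥ 5), with A ~ Bin(20 − m, p) and B ~ Bin(m, q). Type I error uses p = 0.10 and power uses p = 0.30. For q I take 0 as a floor, 0.13 (the partial-response rate for this regimen in CRC in Section 2.8) and 4/23 = 0.174 (Section 2.6.1). Cells show type I error / power.

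| m | q = 0 | q = 0.13 | q = 0.174 |
|---|---|---|---|
| 0 | 0.043 / 0.762 | 0.043 / 0.762 | 0.043 / 0.762 |
| 1 | 0.035 / 0.718 | 0.046 / 0.737 | 0.049 / 0.744 |
| 2 | 0.028 / 0.667 | 0.048 / 0.710 | 0.056 / 0.724 |
| 3 | 0.022 / 0.611 | 0.051 / 0.681 | 0.063 / 0.703 |

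The type I error can move either way, and power falls throughout because each q is below 0.30. One such patient has a small effect. The documents give no value for m.

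**The case against.** The best defense is that the item can only sensibly mean a second malignancy. A protocol that requires an advanced tumor cannot intend to bar everyone who has one, and no site would apply it that way. This is a fair account of practice. A reader might infer from the literal text that the trial can enroll nobody, but the inclusion and basket criteria show plainly who is meant to enter. It would also be wrong to claim both harms together: the contradiction belongs to the literal reading and the CRC opening to the practical one.

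The second defense is that enrolling a patient with active CRC is unlikely. The three-year limb could be used against it, and Section 5.4.2 bars other cancer treatment while on study, so a second cancer that needs treatment would be hard to accommodate. This also stands in part. It makes admission less likely, but it does not remove the written exemption.

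A reader might further infer that CRC lesions cannot be told apart on imaging from small bowel or appendiceal metastases, so that responses would be credited to the wrong tumor. The documents do not say so. Section 5.1.1 requires a tissue diagnosis, and Appendix 8 plans a pathological diagnosis of study specimens, although neither types every lesion. What can be said is that attribution may be difficult and the recorded response could be affected.

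**Conclusion.** The criterion is wrong as written in both places: it exempts a tumor the trial does not study and exempts none that it does. That conclusion needs no assumption beyond the text. The wording may have been carried over from a CRC protocol. Section 5.3.4 mentions a rising CEA level and treatment arms in a single-arm trial, and Section 2.4.2.3 carries another protocol's number. This is inference and the conclusion does not depend on it.

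The effect on the results is possible, unquantified and probably small. It requires that a patient with concurrent active CRC is enrolled and that the CRC lesions alter the recorded response. The documents give no frequency for either step. A reader might take the chance that a cohort stands one responder short of the cut-off as the chance that this defect changes a conclusion. That is not supported, because such a probability applies only after both steps have occurred. Sample size and power stand as stated. This is an operative eligibility rule that should be corrected, not a flaw in the statistical design.

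**What to change.** In general exclusion 5 of the synopsis and in Section 5.1.2, replace the CRC exemption with *(other than the tumor under study)*. The rule then agrees with the inclusion criterion, and concurrent active CRC is treated like any other second cancer.

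In the same amendment, reconcile the item's three-year look-back with its allowance for other cancers free of disease and treatment for two years. As written, a patient whose earlier cancer ended between two and three years ago is excluded by one sentence and allowed by the next. The protocol should state how the two periods fit together.

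The cost is a few words in two places at the next amendment. No calculation, sample size or analysis changes.

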5.2 METHOD OF TREATMENT ASSIGNMENT

After written informed consent has been obtained and eligibility established, each patient will be assigned an identification number and enrolled on study and will receive study medications in this single-arm study.

5.3 STUDY TREATMENT

This is a phase IIA, open-label study of cobimetinib and atezolizumab. All patients enrolled on study will receive cobimetinib 60 mg orally on Days 1–21 plus atezolizumab 840 mg IV on Day 1 and Day 15 in a 28-day cycle. For patient who have discontinued cobimetinib, atezolizumab can be given IV at 1680 mg once every 4 weeks.

The Investigator of the study will ensure maintenance of complete and accurate records of the receipt, dispensation, and disposal or return of all atezolizumab and cobimetinib in accordance with 21 Code of Federal Regulations (CFR), Part 312.57 and 312.62 and Genentech requirements.

5.3.1 Atezolizumab Dosage, Storage, and Administration

The Atezolizumab is 840 mg drug product will be supplied in a single-use, 15 mL USP/Ph. EUR. Type 1 glass vial as a colorless to slightly yellow, sterile, preservative-free clear liquid solution intended for IV administration. Atezolizumab will be administered in a monitored setting where there is immediate access to trained personnel and adequate equipment/medicine to manage potentially serious reactions.

For more detailed information on drug preparation, storage, and administration, refer to the Investigator's Brochure. Atezolizumab will be supplied by Genentech Inc. The vial is designed to deliver 14 mL (840 mg) of atezolizumab solution, but may contain more than the stated volume to enable delivery of the entire 14 mL volume. The formulation of atezolizumab 840 mg drug product is identical to that of atezolizumab 1200 mg drug product.

Atezolizumab infusions will be administered per the instructions outlined in Table 1.

Table 1: Administration of First and Subsequent Infusions of Atezolizumab

First Infusion	Subsequent Infusions
Premedication is allowed.	If patient experienced IRR during any previous infusion, pre-medication with antihistamines may be administered for Cycles ≥ 2 at the discretion of the treating physician.
Record vital signs (HR, RR, BP, and T) within 60 min before starting infusion.	Record patient's vital signs (HR, RR, BP, and T) within 60 min before starting infusion.
Infuse atezolizumab (one vial in 250 mL NaCl) over 60 (± 15) min	If the patient tolerated the first infusion well without infusion-associated AEs, the second infusion may be delivered over 30 (± 10) min.

Record vital signs (HR, RR, BP, and T) during the infusion at 15, 30, 45, and 60 min (\pm 10-min windows are allowed for all timepoints).	If the patient had an IRR during the previous infusion, the subsequent infusion must be delivered over 60 (\pm 15) min.
Record patient's vital signs (HR, RR, BP, and T) at 30 (\pm 10) min after the infusion.	Record patient's vital signs (HR, RR, BP, and T) during the infusion if clinically indicated or patient experienced symptoms during the previous infusion.
Patients will be informed about the possibility of delayed post-infusion symptoms and instructed to contact their study physician if they develop such symptoms.	Record patient's vital signs (HR, RR, BP, and T) at 30 (\pm 10) min after the infusion, if clinically indicated or patient experienced symptoms during previous infusion. If no reaction occurs, continue subsequent infusions over 30 (\pm 10) min with same schedule for recording vital signs.

Abbreviations: AE = adverse event; BP = blood pressure; HR = heart rate; IRR = infusion-related reaction; NaCl = sodium chloride; RR = respiratory rate; T = temperature

Guidelines for treatment interruption or discontinuation and the management of specific adverse events are provided in Section 5.5, Appendix 7 as well as the atezolizumab Investigator's Brochure. For anaphylaxis precautions, see Appendix 8.

See the Investigator's Brochure for detailed instructions on drug preparation, storage, and administration.

Any overdose or incorrect administration of study drug should be noted on the Study Drug Administration eCRF. Adverse events associated with an overdose or incorrect administration of study drug should be recorded on the Adverse Event eCRF (See Section 6.3).

Atezolizumab may be prepared, handled, and administered per the current FDA-approved package insert.

